#### 4.6.3. Definitions of Absolute Standardized Differences

Balance is evaluated using absolute standardized differences [12]. When evaluating balance before any covariate balancing for continuous covariates for the subject device (s) and comparator device (c) we use  $\hat{d} = \frac{|\bar{x}_s - \bar{x}_c|}{\sqrt{\frac{\hat{v}(\bar{x}_s) + \hat{v}(\bar{x}_c)}{2}}}$  and for binary covariates  $\hat{d} = \frac{|\hat{p}_s - \hat{p}_c|}{\sqrt{\frac{\hat{p}_s(1-\hat{p}_s) + \hat{p}_c(1-\hat{p}_c)}{2}}}$ .

When using weights, covariate balance for a continuous covariate we replace the means and variance of the comparator group with weighted versions of those estimates [13]  $\hat{d}^w = \frac{|\bar{x}_s - \bar{x}_c^w|}{\sqrt{\frac{\hat{v}(\bar{x}_s) + \hat{v}^w(\bar{x}_c)}{2}}}$ , where  $\bar{x}_c^w = \frac{\sum_{i=1}^{n_c} w_i x_i}{\sum_{i=1}^{n_c} w_i}$ ,  $\hat{v}^w(\bar{x}_c) = \frac{\sum_{i=1}^{n_c} w_i}{(\sum_{i=1}^{n_c} w_i)^2 - \sum_{i=1}^{n_c} w_i^2} \sum_{i=1}^{n_c} w_i (x_i - \bar{x}_c^w)^2$ . For a categorical covariate we replace the proportion of the comparator group with a weighted version of that estimate [18]  $\hat{d}^w = \frac{|\hat{p}_s - \hat{p}_c^w|}{\sqrt{\frac{\hat{p}_s(1-\hat{p}_s) + \hat{p}_c^w(1-\hat{p}_c^w)}{2}}}$ , where  $\hat{p}_c^w = \frac{\sum_{i=1}^{n_c} w_i x_i}{\sum_{i=1}^{n_c} w_i}$ .

Nominal variables with more than two categories are summarized using generalizations of the above for binary covariates [14].

#### 4.7 Outcome Analysis

For persistent AF, the primary objective is to estimate the covariate balanced risk difference comparing the subject device and the comparator device within each data source and

subsequently averaged across data sources, with the average used for hypothesis testing of non-inferiority for the safety endpoint. Additionally, descriptive analyses for the safety endpoint will be conducted (e.g., unbalanced outcome analysis), as well as exploratory analyses (1.2).

For ischemic VT, the primary objective is to estimate the proportion of patients with safety events who received ThermoCool STSF (unbalanced data), pooled across the two data sources and used to compare against a performance goal for hypothesis testing purposes, following the recommendations of Lu et al [8], since covariate balance was not achieved through propensity score balancing approaches. Descriptive analyses for the safety endpoint will be conducted (e.g., proportion with safety events within catheter group and within data source). Descriptive analyses for the safety endpoint will be conducted in patients who received ThermoCool ST for contextualizing the ThermoCool STSF results. Additional exploratory analyses will also be conducted (1.2).

#### 4.7.1 Method for Estimating a Crude Risk and Risk Difference for Persistent AF

The Kaplan Meier estimate of survival is:

$$\hat{S}(t) = \begin{cases} 1 & \text{If } t < t_1 \\ \prod_{t_j \leq t} \left(1 - \frac{d_j}{Y_j}\right) & \text{If } t_j \leq t \end{cases}$$

for times  $t_1, t_2 \dots t_D$  for  $D$  distinct times, with  $d_j$  events at time  $j$  and  $Y_j$  patients at risk.

The crude risk is defined for either the subject device group or comparator device group as  $\widehat{CI} = 1 - \hat{S}(t)$ , with  $\hat{S}(t)$  denoting the Kaplan Meier estimate of survival for  $t=90$  days. The variance of the crude risk is represented as  $\widehat{\text{var}}(\widehat{CI})$ , using the Greenwood estimate of the variance. The two-sided 90% Wald confidence interval is:  $\widehat{CI} \pm Z_{1-0.05} * \widehat{SE}_{\widehat{CI}}$ , where  $\widehat{SE}_{\widehat{CI}} = \sqrt{\widehat{\text{var}}(\widehat{CI})}$ .

The crude risk difference is defined as the difference in the cumulative incidence (CI) between the subject device group and the comparator device group at 90 days. Specifically, the estimated crude risk difference is represented in the subject device group (s; ThermoCool ST) and comparator device group (c; ThermoCool STSF) as  $\widehat{\Delta} = \widehat{CI}_s - \widehat{CI}_c$ , where  $\widehat{CI} = 1 - \hat{S}(t)$ , with  $\hat{S}(t)$  denoting the Kaplan Meier estimate of survival for  $t=90$  days. The variance of the crude risk difference is calculated as  $\widehat{\text{var}}(\widehat{\Delta}) = \widehat{\text{var}}(\widehat{CI}_s) + \widehat{\text{var}}(\widehat{CI}_c)$ , where each variance term is the Greenwood estimate of the variance. The two-sided 90% Wald confidence interval for the difference is:  $\widehat{\Delta} \pm Z_{1-0.05} * \widehat{SE}_{\widehat{\Delta}}$ , where  $\widehat{SE}_{\widehat{\Delta}} = \sqrt{\widehat{\text{var}}(\widehat{\Delta})}$ . All confidence intervals described in this section are for descriptive reporting of results, not hypothesis testing.

#### 4.7.2 Method for Estimating a Covariate Balanced Risk and Risk Difference for Persistent AF

First, the propensity score is calculated for each patient (section 4.6.1). In the subject device arm, patients receive a weight of 1, therefore the estimate of survival is the conventional Kaplan

Meier estimator described above (section 4.7.1). In the comparator arm, patients receive unequal weights  $\neq 1$ , therefore a weighted Kaplan Meier estimator is used to calculate survival [15]:

$$\hat{S}^w(t) = \begin{cases} 1 & \text{If } t < t_1 \\ \prod_{t_j \leq t} \left(1 - \frac{d_j^w}{Y_j^w}\right) & \text{If } t_j \leq t \end{cases}$$

where  $w_i = \frac{\hat{e}_i}{1-\hat{e}_i}$ ,  $\hat{e}_i$ = estimated propensity score for patient  $i = 1, \dots, n_c$ ,  $d_j^w = \sum_{i:T_i=t_j} w_i \delta_i$ ,  $Y_j^w = \sum_{i:T_i \geq t_j} w_i$ , where  $T_i$  is a right-censored event time and  $\delta_i$  is an event indicator,  $\delta_i = 1$  if  $T_i$  corresponds to an event and  $\delta_i = 0$  if  $T_i$  is censored.

A point estimate of the covariate balanced risk difference is calculated as  $\hat{\Delta} = \widehat{CI}_s - \widehat{CI}_c$ , where  $\widehat{CI}_s = 1 - \hat{S}(90)$ ,  $\widehat{CI}_c = 1 - \hat{S}^w(90)$ , with  $\hat{S}(90)$  denoting the Kaplan Meier estimate of survival and  $\hat{S}^w(90)$  the weighted Kaplan Meier estimate of survival at 90 days. The variance of the covariate balanced risk difference is calculated as  $\widehat{var}(\hat{\Delta}) = \widehat{var}(\widehat{CI}_s) + \widehat{var}(\widehat{CI}_c)$ , where  $\widehat{var}(\widehat{CI}_s) = \widehat{var}(\hat{S}(90))$  and  $\widehat{var}(\widehat{CI}_c) = \widehat{var}(\hat{S}^w(90))$ . Estimation of the variance corresponding to the survival estimates in the subject device group,  $\widehat{var}(\widehat{CI}_s)$ , is based on a conventional greenwood estimate because all patients receive a weight of 1. Estimation of the variance corresponding to the survival estimates in the comparator device group,  $\widehat{var}(\widehat{CI}_c)$ , is based on an infinitesimal jackknife [17, 18] because patients do not receive the same weight of 1. The two-sided 90% Wald confidence interval for the difference is:  $\hat{\Delta} \pm Z_{1-0.05} * \widehat{SE}_{\hat{\Delta}}$ , where  $\widehat{SE}_{\hat{\Delta}} = \sqrt{\widehat{var}(\hat{\Delta})}$ . The two-sided 90% Wald confidence interval within each catheter group is:  $\widehat{CI} \pm Z_{1-0.05} * \widehat{SE}_{\widehat{CI}}$ , where  $\widehat{SE}_{\widehat{CI}} = \sqrt{\widehat{var}(\widehat{CI})}$ . All confidence intervals described in this section are for descriptive reporting of results, not hypothesis testing.

#### 4.7.3 Pooling of Risk Differences Across Data Sources for Persistent AF

The approach to pooling effect estimates (i.e., risk differences) is based on fixed-effect or common-effect model, in which a common effect is assumed across data sources. The choice of a fixed-effect model (vs. a random-effects model) is based on several considerations as highlighted by the American Heart Association: “The choice of a fixed-effect model (ie, inverse variance pooling) should be based on 2 important factors: whether the included studies are functionally identical, meaning they include similar or nearly identical populations, interventions, and methods, and whether the goal of synthesis of results across studies is to compute a common effect size that is applicable to populations similar or identical to those included but not generalizable to other populations.” [19] The types of inferences desired in this context are more consistent with a fixed-effect model, insofar as inferences apply to “*this* collection of studies and say nothing about other studies that may be done later, could have been done earlier, or may have already been done...” [20]. The argument about the nature of inferences is independent of one about effect heterogeneity. An argument for a fixed-effect model based on heterogeneity can be made in this application based on the harmonized approach to study design, in which the inclusion/exclusion criteria, treatment groups, covariates and outcome measurement are the same (or approximately so) across the data sources. In addition, given the relatively small number of studies a fixed-effect model is more compelling because a random-effects model requires a Bayesian approach that assumes a particular underlying effect

size distribution or a frequentist approach with modifications to calculation of the standard error and critical values (based on a t-distribution) that can result in extremely wide confidence intervals in order to obtain reasonable coverage [21, 22].

Calculating the average treatment effect from a fixed-effect model is straightforward [23]. For each data source ( $q = 1, 2$ ) we estimate the risk difference,  $\hat{\Delta}_q$  (section 4.7.1). The variance of this estimate is denoted by  $\widehat{\text{var}}(\hat{\Delta}_q)$  and a weight is constructed by taking the inverse of this quantity,  $w_q = \frac{1}{\widehat{\text{var}}(\hat{\Delta}_q)}$ . The average treatment effect across studies is then estimated using a weighted mean,  $\hat{\bar{\Delta}} = \frac{\sum_{q=1}^2 w_q \hat{\Delta}_q}{\sum_{q=1}^2 w_q}$ . The variance of this weighted mean is then  $\widehat{\text{var}}(\hat{\bar{\Delta}}) = \frac{1}{\sum_{q=1}^2 w_q}$  and the standard error is  $\widehat{SE}(\hat{\bar{\Delta}}) = \sqrt{\widehat{\text{var}}(\hat{\bar{\Delta}})}$ . The two-sided 90% Wald confidence intervals is:  $\hat{\bar{\Delta}} \pm Z_{1-0.05} * \widehat{SE}_{\hat{\bar{\Delta}}}$ . This is the only confidence interval used for hypothesis testing for the persistent AF population.

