### 1.1 Primary Objectives

The primary objectives are:

- 1) To evaluate the non-inferiority of ablation with the ThermoCool ST catheter relative to the ThermoCool STSF catheter for the treatment of persistent AF on a composite safety endpoint.
- 2) To evaluate ablation with the ThermoCool STSF catheter relative to a performance goal for the treatment of ischemic VT on a composite safety endpoint.

Determinations about non-inferiority with respect to safety for the first objective (persistent AF) will be based on a hypothesis test of the subject device relative to the comparator device with respect to absolute risk (i.e., risk difference) using data balanced on pre-specified measured covariates. Hypothesis testing for the second objective (ischemic VT) will compare the cumulative incidence of a composite safety endpoint in the subject device group to a performance goal using unadjusted data.

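### Section 4.7.3 takes the input to the only persistent AF test interval from the crude analysis (4.7.1), contradicting the sections that put the test on the covariate-balanced difference (4.7.2)

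*SAP*

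**What the plan says.** Section 4.7.3 is the operative rule for the persistent AF test. For each data source it takes the risk difference from "section 4.7.1). The variance of this estimate is denoted by" and then forms the inverse-variance weights, the weighted mean and a 90% Wald interval. It says of that interval: "This is the only confidence interval used for hypothesis testing for the persistent AF population".

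The section it cites is headed "Method for Estimating a Crude Risk and Risk Difference for Persistent AF". That section uses ordinary Kaplan-Meier estimates in both arms, with Greenwood variances. The weighted version follows in 4.7.2, which begins its definition with "A point estimate of the covariate balanced risk difference is calculated as" and uses a Greenwood variance for ST and an infinitesimal jackknife variance for STSF. Section 4.7.3 does not mention 4.7.2.

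Elsewhere the SAP describes the test differently:

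- Section 1.1 bases the AF non-inferiority decision on a risk difference "using data balanced on pre-specified measured covariates".
- Section 4.7 says that "the primary objective is to estimate the covariate balanced risk difference comparing the subject device and the comparator device within each data source", and that this is "subsequently averaged across data sources, with the average used for hypothesis testing of non-inferiority for the safety endpoint".
- Section 1.2, for the bed-size sensitivity analysis, reruns the balanced analysis in Mayo and recomputes the average from it.
- The Table 5 shell (balanced data) has the pooling weights, the average difference and its p-value. The Table 4 shell (unbalanced data) has none of these.

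**The concern.** The sentence that fixes the input to the confirmatory interval names a different estimator from the one the objectives require, and nothing later in the chain corrects it. Section 4.8 describes the tested quantity as a difference in cumulative incidence averaged over the two sources, does not say whether it is balanced, and refers back to 4.7.3. Sections 4.7.1 and 4.7.2 use the same symbol for the difference and for its variance, so the pooling formula fits either.

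Both differences will be computed in each source, for Tables 4 and 5, so both will be available to pool. Section 4.5 gives the pooling to one person at Mercy and points to 4.7.3 for the method. Followed literally, 4.7.3 would rest the non-inferiority decision on a confounded comparison. Left unresolved, it leaves room to choose between two estimates after outcomes are linked, which the separation of design from analysis in 4.5 is meant to prevent.

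**Working it through.** **1. The plan's own figure.** Section 3 gives N = 330 for risk 0.07 in both arms, margin 0.07, one-sided alpha 0.05 and power above 80%.

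n per arm = (1.645 + 0.842)² × 2 × 0.07 × 0.93 / 0.07² = 164.3, rounded up to 165, so 330 in total. Power is 80.2% at 165 per arm and 79.9% at 164. The figure reproduces and does not depend on which section 4.7.3 cites.

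**2. Tracing the references.** 4.8 → 4.7.3 → 4.7.1 (crude). Sections 1.1, 1.2 and 4.7 and Table 5 → balanced, which is 4.7.2. The two routes end at different estimators.

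The sentence closing 4.7.1, "All confidence intervals described in this section are for descriptive reporting of results, not hypothesis testing", does not decide between them, because 4.7.2 closes with the same sentence about its own intervals.

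**3. How far the two inputs differ in balance.** Absolute standardized differences (ASD) from Appendix Tables 1 and 2, crude versus the selected weights (trimmed at the 95th percentile):

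| Covariate | Crude | Trimmed 95 |
|---|---|---|
| Mercy index year | 1.991 | 0.059 |
| Mercy operator volume | 0.759 | 0.277 |
| Mayo hospital beds | 3.012 | 1.599 |
| Mayo electrical cardioversion | 0.551 | 0.458 |
| Mayo covariates with ASD > 0.20 | 14 | 6 |

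**4. How far they differ in precision.** Inputs: Table 1 (Mercy 186 ST and 763 STSF; Mayo 337 ST and 164 STSF) and risk 0.07, ignoring censoring. Per source, var = 0.07 × 0.93 × (1/n_ST + 1/n_STSF). Pooled SE = 1/√(Σ 1/var).

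Crude:
- Mercy: 0.0651 × (1/186 + 1/763) = 0.000435, SE 0.0209
- Mayo: 0.0651 × (1/337 + 1/164) = 0.000590, SE 0.0243
- Pooled SE 0.0158, source weights 58% Mercy and 42% Mayo

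Balanced: the SAP gives no effective sample size for the weighted comparator arm. As an assumption, n_STSF is replaced by a fraction of its nominal value in both sources. Power is Φ(0.07/SE − 1.645) at a true difference of zero.

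| Assumed fraction | Pooled SE | Mercy weight | Mayo weight | Power |
|---|---|---|---|---|
| 100% (crude) | 0.0158 | 58% | 42% | 99.7% |
| 50% | 0.0185 | 65% | 35% | 98% |
| 25% | 0.0223 | 72% | 28% | 93% |
| 10% | 0.0306 | 78% | 22% | 74% |

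The cited section therefore affects the point estimate, the standard error and the relative weight of the two sources.

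**The case against.** The strongest reply is that the intention is plain. The primary objective, the outcome-analysis overview, the bed-size sensitivity analysis and the Table 5 shell all agree. Section 4.6 also describes balancing within each source followed by pooling, and section 4.7 calls the unbalanced analysis descriptive. A pooled crude result has no place in the safety table shells. One section number in parentheses does not outweigh all this.

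That stands as far as intent goes. A reader of 4.7.3 and 4.8 alone might infer that the primary AF test is planned as unadjusted; the document as a whole does not support this. It does not make the reference harmless, since the error lies in the sentence that defines the test input.

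Two further inferences also fail:

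- That the interval would be too narrow because Greenwood ignores the weighting. If 4.7.1 were followed there would be no weights, and Greenwood is the right variance for that estimator. The fault would be the wrong quantity, not a wrong variance for it. Nor can one percentage be put on the gap in precision, because it depends on an effective sample size that the SAP does not report.
- That all the crude imbalance is at stake. Much of it in Mayo remains under the planned weights: bed size still stands at 1.599 and electrical cardioversion at 0.458. Correcting the reference does not remove that part.

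**Conclusion.** The contradiction is real and should be corrected before outcomes are linked. Section 4.7.3 cites the crude estimate and variance for the sole AF test interval, against sections 1.1, 1.2 and 4.7 and Table 5. It is best read as a wrong cross-reference, not as a decision to test unadjusted data.

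The choice of input matters most clearly in Mercy, where weighting nearly removes the index-year imbalance and cuts that in operator volume by more than half. In Mayo it improves balance only in part. The crude pooled SE of about 0.016 compares with about 0.019 to 0.031 for the balanced analysis. That range rests on a 7% risk, no censoring, and an effective comparator sample size assumed at 50% to 10% of nominal. No figure stated in the SAP changes.

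**What to change.** In section 4.7.3, change the cross-reference from 4.7.1 to 4.7.2. Add a sentence saying that the per-source estimate and variance to be pooled are the covariate-balanced ones: comparator ATT weights trimmed at the 95th percentile as in 4.6.2, with Greenwood variance for ST plus infinitesimal jackknife variance for STSF. Naming the trimming is useful because 4.7.2 prints the weight formula without repeating it. Using the word balanced in 4.8 would close the chain. A separate symbol for the crude difference in 4.7.1 is optional.

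The cost is one section number and one or two sentences. Sample size, margin, table shells and programming of the intended analysis are unchanged.

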### 3. Sample Size Justification

Sample size calculations are based on statistical power for the primary objectives (i.e., safety analyses) proposed in this study. The minimum required sample size was calculated separately for the planned hypothesis tests of non-inferiority of the composite safety endpoint in the persistent AF cohort and ischemic VT cohorts. Below are the details of power calculations.

For persistent AF, hypothesis tests are based on two-group comparison data pooled across data sources using the upper bound of the two-sided 90% Wald confidence interval (section 4.7.3). For this reason, power calculations use a two-sample test for a difference in proportions based on a Pearson chi-square test as implemented in PROC POWER in SAS, version 9.4. For persistent AF, we assume the composite safety endpoint proportion is 0.07 in both arms (i.e., an assumed population difference in proportions of 0), a non-inferiority margin of 0.07, and a one-sided test at the 0.05 alpha-level to determine the minimal N which provided more than 80% power; this sample size was 330 (or 165 per group).

For ischemic VT, hypothesis testing is based on a single group (ThermoCool STSF) with data pooled across the two data sources using the upper bound of the two-sided 90% confidence interval for a one-sample exact test of a proportion (section 4.7.4). For this reason, power calculations use a one-sample exact test for a proportion as implemented in PROC POWER in SAS, version 9.4. For ischemic VT, we assume the composite safety endpoint proportion is 0.075, a performance goal of 0.15, and a one-sided test at the 0.05 alpha-level. Given the sample size of 70 (Table 1), the estimated power is 57%.

Based on the sample sizes available (Table 1), the study is likely adequately powered for persistent AF, but less than adequately powered for ischemic VT.

Table 1. Available Sample Sizes for Each Study Population After Inclusion/Exclusion Criteria Are Applied

|                                    | ST (test)   | STSF (comparator) |
|------------------------------------|--------------------|--------------------------|
| Persistent AF               |                    |                          |
| Mercy                              | 186                | 763                      |
| Mayo Clinic                        | 337                | 164                      |
| Total                       | 523                | 927                      |

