#### 4.6.2 Method for Covariate Balancing

We considered several PS methods to maximize balance [7] (see appendix, tables 1-4). For ischemic VT, none of the methods considered adequately balanced the data, therefore a comparative design was not pursued in favor of single arm design using a performance goal [8]. For persistent AF a singular method that minimizes imbalance across the two data sources was selected, average treatment effect on the treated weights [9] with weight trimming/winsorizing [10]. Specifically, patients receiving the subject device receive a weight of 1 and those receiving the comparator device (c) receive a weight based on the odds,  $w_i = \frac{\hat{e}_i}{1-\hat{e}_i}$ , where  $\hat{e}_i$  = estimated propensity score for patient  $i = 1, \dots, n_c$ . Furthermore, patient weights in the comparator group only are trimmed/winsorized at the 95th percentile of the weight distribution (i.e., all weights with value above the 95th percentile are set equal to the 95th percentile).

When used with logistic regression to estimate the propensity score, weight trimming has been shown to reduce bias in estimating the treatment effect when the model is mis-specified due to non-linear and non-additive effects, as well as to increase precision of the estimated treatment effects [10]. Use of untrimmed ATT weights has been shown unbiased in simulation studies in estimating the risk difference using survival data [11].

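### Pooling the two AF risk differences by inverse estimated variance biases the estimate against ST and understates its standard error; source weights based on effective sample size avoid both

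*SAP*

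**What the plan says.** Section 4.7.3 estimates a risk difference Δ_q and its variance in each source (q = Mercy, Mayo), "and a weight is constructed by taking the inverse of this quantity". The pooled difference is the weighted mean, and its variance is 1/Σw_q. On the resulting 90% Wald interval the section says: "This is the only confidence interval used for hypothesis testing for the persistent AF population". Section 4.8 compares the upper bound with the margin of 0.07.

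Section 4.7.3 points to section 4.7.1 for Δ_q, but section 4.7 and Table 5 show that the covariate-balanced difference of section 4.7.2 is meant. There the ST arm has weights of 1 and a Greenwood variance. The STSF arm has odds weights, and section 4.6.2 adds that "patient weights in the comparator group only are trimmed/winsorized at the 95"th percentile. The STSF variance "is based on an infinitesimal jackknife [17, 18] because patients do not receive the same weight of 1". It is therefore a function of the observed weighted events.

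Section 4.7.3 argues at length for a fixed-effect over a random-effects model. It does not discuss dependence between an estimate and its estimated weight. No ESS is given anywhere.

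**The concern.** The estimated variance of a small proportion rises with the proportion. If STSF happens to have few weighted events in one source, that source's ST minus STSF difference is too high, its estimated variance is too small, and inverse-variance pooling gives it extra weight. If STSF happens to have many events, the source is down-weighted. These errors do not cancel, so the pooled difference drifts upward, against ST, even when each source's own estimate is unbiased. Chance-low ST risk pulls the other way, but the ST arm is unweighted and, in Mayo, much the larger arm in effective terms, so the comparator effect prevails. In addition, 1/Σw_q treats random weights as fixed.

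At stake are the primary safety estimate for a label expansion and the only interval that decides it.

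**Working it through.** **The plan's own figure.** Section 3 takes a 7% event risk in each arm and a 7-point margin, and specifies "a one-sided test at the 0.05 alpha-level to determine the minimal N which provided more than 80% power; this sample size was 330". With an unpooled variance, n per arm = (1.645 + 0.842)² × 2 × 0.07 × 0.93 / 0.07² = 164.3, so 165 per arm and 330 in total (power 80.15%). This reproduces. It assumes unweighted patients in a single comparison.

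**Inputs.** From section 3, Table 1: Mercy 186 ST and 763 STSF; Mayo 337 ST and 164 STSF. From the Appendix balance tables: in Mayo, hospitals with at least 500 beds account for 10 of 164 STSF and 301 of 337 ST patients, with a standardized difference of 1.599 after trimming at 95; in Mercy, index year 2014-18 accounts for 184 of 763 STSF and 174 of 186 ST patients, with 0.059 after trimming at 95.

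**Upper limits on comparator ESS**, where ESS = (Σw)²/Σw².
- Mayo: with an ST share of 301/337 = 0.893, a difference of 1.599 implies a weighted STSF share of about 0.278, carried by 10 patients. Equal weights within bed-size groups give the largest possible ESS: 1/(0.278²/10 + 0.722²/154) ≈ 90. At 7% risk those 10 patients have no event with probability 0.93¹⁰ = 48%.
- Mercy: a difference of 0.059 from 174/186 = 0.935 implies a weighted share of about 0.920, so ESS is at most 1/(0.920²/184 + 0.080²/579) ≈ 217.

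**The mechanism in one example** (assumed ESS: Mercy 217, Mayo 50; all other risks at 7%).
- Mercy variance: 0.0651/186 + 0.0651/217 = 0.00065.
- Mayo, observed STSF risk 7%: 0.0651/337 + 0.0651/50 = 0.00150; Mayo's share of the pooling weight is 30%.
- Mayo, observed STSF risk 2% (Δ too high by 5 points): 0.00019 + 0.0196/50 = 0.00059; share 53%.
- Mayo, observed STSF risk 12% (Δ too low by 5 points): 0.00019 + 0.1056/50 = 0.00231; share 22%.

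Errors of equal size in opposite directions receive 53% and 22% of the weight.

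**Simulation.** 20,000 to 40,000 runs per setting, Table 1 counts, 7% STSF risk in both sources, binary outcome. Comparator weights are fixed, lognormal in shape and winsorized at the 95th percentile to give the stated ESS. Variance is the Bernoulli variance (ST) plus Σw²(y−p)² with normalised weights (STSF). ESS-based weights are a_q ∝ 1/(1/ESS_ST,q + 1/ESS_STSF,q). All columns are at true difference 0 except rejection at the margin, where the true difference is 0.07.

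| Assumed STSF ESS, Mercy/Mayo | Bias, points (inverse variance) | 90% CI coverage (inverse variance) | Lower bound above truth | Upper bound below truth | Rejection at margin | Power, inverse variance vs ESS weights | Coverage, ESS weights |
|---|---|---|---|---|---|---|---|
| 217/90 (best case) | +0.2 to +0.3 | 87% | 9% | 4% | 4% | 98% vs 98% | 90% |
| 217/50 | +0.5 | 82% | 15% | 3-4% | 4% | 95% vs 96% | 89% |
| 217/30 | +0.9 | 73-75% | 22% | 3% | 4% | 91% vs 94% | 89-90% |
| 120/25 | +1.2 | 69% | 28% | 2-3% | 3% | 82% vs 89% | 89% |

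At 217/30 the inverse-variance estimate has an actual SD of 0.0252 against a mean reported SE of 0.0200. With ESS-based weights the figures are 0.0225 and 0.0222, and bias is about 0 in every row. On unweighted data, inverse-variance pooling covers 88.6-89.3% with bias about 0, so the trouble comes from combining it with heavily weighted comparators.

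**Other outcome-free weights.** Weights by ST count give Mayo 337/523 = 64%, against 22% under ESS weights at 217/30. They remove the bias but leave coverage at about 75-88%, because Mayo's own jackknife Wald interval covers only about 72-86% at ESS 25-60.

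**The case against.** The strongest reply is that the decision uses only the upper bound, and the upper bound is safe: it falls below the truth in about 3-4% of runs against a nominal 5%. A reader who sees coverage of 75% might infer a risk of false non-inferiority. The calculations do not support that; at the margin the test is conservative. This part of the objection stands in full. Power also stays above the plan's 80% in every setting run, and the bias is small beside a 7-point margin.

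The ESS is also assumed. The balance tables give an upper limit for Mayo, not a value, and the best case costs only about 3 points of coverage. No single coverage figure can be attributed to the plan. This stands too, and it is why the result is given as a range.

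Finally, inverse-variance fixed-effect pooling is standard, cited and prespecified. That is true, but the SAP's argument concerns the choice of effect model and does not address the dependence of the weights on the outcomes. The two-sided interval and point estimate will be reported in Table 5 and read as the safety result, so their bias and understated error matter even when the test itself is protected.

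**Conclusion.** The point holds as a correctable weakness of the primary AF estimate. Inverse-variance pooling makes ST look worse by about 0.2 to 0.9 percentage point for a Mayo comparator ESS of 90 down to 30, and reduces 90% coverage to between about 87% and 73-75%. The harm is a biased estimate, a lower bound that too often suggests excess risk with ST, and a power loss of about 0 to 4 points in most settings and up to about 7 at the lowest ESS tried. It is not a route to a false claim of non-inferiority.

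A reader might also infer that any weights fixed in advance would cure the problem. They would not: coverage is restored to 88-90% with ESS-based weights but not with weights by ST count.

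The figures assume 7% comparator risk in both sources, no censoring, no residual confounding, a common effect, and fixed lognormal-shaped weights at the stated ESS.

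**What to change.** In section 4.7.3, before outcomes are linked:

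1. Compute and report ESS = (Σw)²/Σw² for each arm and source from the winsorized weights. For ST this equals the count (186 and 337). The outcome-removed datasets described in section 4.5 suffice.
2. Fix source weights a_q ∝ 1/(1/ESS_ST,q + 1/ESS_STSF,q), normalised to sum to 1.
3. Make Σ a_q Δ_q the primary pooled difference, with variance Σ a_q² var(Δ_q), and use its 90% Wald interval for the test in section 4.8.
4. Keep inverse-variance pooling as a sensitivity analysis.
5. State the assumed ESS beside any coverage or power figure.

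The cost is two formulas and a departure from the cited pooling formula. Power was equal or higher in every setting run, and the Table 5 weights become known at the design stage. The change does not repair Mayo's own source-level interval, which stays poor at low ESS and should be read with that in mind.
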